9.2.3. Planned Analyses

At least three analyses will be conducted to evaluate the objectives of the protocol after all subjects have completed their visits at Week 24, Week 48 and Week 96, respectively. Further data cuts and analyses may be conducted as necessary in order to support regulatory submissions and publications (first publication at Week 48). The Week 48 analysis will be primary and no results will be shared publicly until Week 48 analysis is complete. Full details for the primary Week 48 analysis (and preliminary Week 24

analysis) will be prespecified in the RAP prior to the database freeze for the Week 24 analysis and sponsor review of any summary of data grouped by actual treatment arm.

9.2.3.1. Week 24 data analyses

An analysis of data through Week 24 will be conducted when all subjects have completed their Week 24 visit, with the intent of expediting submission of results to health authorities.

The analyses described in Section 9.3.2.2, Section 9.3.3 and Section 9.3.6 will be performed. Health outcomes analyses will not be performed.

There is no intention to stop the study early if positive efficacy findings are seen at Week 24 and a formal hypothesis test of non-inferiority at Week 24 will not be evaluated. The analysis at Week 48 is primary and will overrule the findings based on the Week 24 data. Therefore, no multiplicity adjustment to the primary Week 48 treatment comparisons is needed because of the analysis of Week 24 data.

Neither investigators nor subjects will be informed of the results of the Week 24 data analysis. Sponsor staff will only review aggregate data by actual treatment arm after the Week 24 IDMC evaluation is complete as required in the preparation of submission documents.

9.2.3.2. IDMC analyses

Independent review will be provided by an IDMC to ensure external objective medical and/or statistical review of efficacy and safety in order to protect the ethical interests and well-being of subjects and to protect the scientific validity of this study. An ad-hoc review of data by the IDMC will be triggered whenever the number of confirmed virologic failures in the CAB LA + RPV LA Q8W arm exceeds thresholds pre-specified in the IDMC charter. Further, an interim futility analysis will be performed for the IDMC to evaluate the efficacy and safety of CAB LA + RPV LA Q8W arm when approximately 50% of subjects have completed their visit at Week 24; the sponsor will remain blinded to this analysis. Any additional Week 24 analyses will also be shared with the IDMC. Full details of the methods, timing, decision criteria and operating characteristics will be pre-specified in the IDMC Charter.

Since the statistical stopping guidelines will not result in early stopping due to positive efficacy findings for the Q8W regimen, these planned analyses will not inflate the type I error rate for the primary treatment comparison at Week 48.

9.3. Key Elements of Analysis Plan

9.3.1. Primary Analyses

For the primary efficacy analysis, virologic outcome for each participant in the Intent-to-Treat Exposed population will be calculated according to the FDA's Snapshot algorithm. The primary analysis at Week 48 will take place after the last participant has had their Week 48 viral load assessed, including a retest if required.

As defined by the Snapshot algorithm, HIV-RNA ≥ 50 copies/mL is determined by the last available HIV-1 RNA measurement while the participant is on treatment within the analysis visit window of interest. In addition, participants without evaluable HIV-RNA data for the visit of interest and who discontinue from the maintenance phase for reasons not related to adverse event with HIV-1 RNA result at the time of discontinuation ≥ 50 copies/mL or who change study treatment not permitted per protocol before the analysis window are classified as having HIV-RNA ≥ 50 copies/mL.

For the primary efficacy analysis, the adjusted difference between the randomized arms for the proportion of participants with HIV-1 RNA ≥ 50 c/mL at Week 48 (according to the FDA snapshot algorithm) and its confidence interval will be calculated according to a stratified analysis with Cochran-Mantel Haenszel (CMH) weights. This analysis will adjust for the randomization strata (rederived for analysis to correct for stratification errors) according to prior exposure to CAB + RPV (0 weeks, 1-24 weeks, >24 weeks).

The CMH estimate of the common difference in rates across strata will be calculated as the weighted average of the strata-specific estimates of the difference in proportion between the two arms as follows:

- If n_k is the number of Q8W treated participants, m_k is the number of Q4W arm treated participants, and $N_k = n_k + m_k$ is the total number of participants in the k th stratum, then the CMH estimate is given by

$$\hat{d}_{cmh} = \frac{\sum W_k \hat{d}_k}{\sum W_k}$$

where

$$W_k = \frac{n_k m_k}{N_k}$$

are CMH weights and \hat{d}_k are estimates of the differences in proportions between the two treatment arms, $f_{Q8W} - f_{Q4W}$, for the k th stratum.

The corresponding two-sided 95% CI will be calculated as:

$$\hat{d}_{cmh} \pm 1.96 \times \sqrt{\hat{\text{var}}(\hat{d}_{cmh})}$$

using the variance estimator given by [Sato, 1989], which is consistent in both sparse data and large strata. The formula for computing the Sato variance estimate will be provided in the RAP. Non-inferiority will be declared if the upper bound of the two-sided 95% confidence interval for the difference (Q8W – Q4W) is less than 4%.

The weighted least squares chi-squared statistic [Fleiss, 1981] will be used to assess evidence of treatment difference heterogeneity across strata. strata, Following Lui and

Kelly [Lui, 2000], 0.50 will be added to each cell in any strata for which the stratum-specific rate estimates of either f_{Q8W} or f_{Q4W} are zero or one. Any heterogeneity found to be statistically significant will be explored. Stratum-specific analyses will also be provided. Investigation of heterogeneity will be confined to the primary endpoint. Tests of homogeneity will be assessed at the one-sided 10% level of significance. Full details will be contained in the RAP.

On-treatment data collected from extra visits within a window will be included in the derivation of the Snapshot response/failure but summary tables using observed case (OC) datasets will only use the data captured closest to the target visit date. Detailed explanations of the derivation of visit windows will be included in the RAP. Any changes to the original analysis plan in the protocol will be described in the RAP and/or clinical study report (CSR).

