6.2. Treatment Assignment

Informed consent must be obtained prior to any study procedures, including Screening visit activities. Participants will be assigned to study treatment in accordance with the randomization schedule. The randomization schedule, including stratification, will be generated using the GSK validated randomization software RANDALL NG. The

randomization schedule is comprised of a series of blocks, with equal treatment allocation within each block, which are shared across centers via central randomization. Given the open-label study design, central randomization was used to eliminate selection bias due to foreknowledge of randomized treatment. With central randomization, knowledge at a site of the randomized treatment group for previous subjects does not predict which treatment group will be assigned to the next randomized subject.

Randomization and study treatment assignment will be facilitated by the interactive response technology (IRT) through the central Randomization and Medication Ordering System Next Generation (RAMOS NG).

Following confirmation of fulfillment of study entry criteria, study site personnel will be required to register participants using RAMOS NG for assignment of a unique identifier (designating the participant's randomization code and treatment sequence assignment) for each participant participating in the study. A unique treatment number will be assigned for each participant participating in the study. Participants will be randomized in a 1:1 ratio to CAB LA + RPV LA Q4W or to CAB LA + RPV LA Q8W in accordance with the computer generated randomization schedule.

Participants who successfully complete 100 weeks of treatment and have a viral load <50 c/ml at Week 96 (or upon retest by Week 100) will be given the opportunity to enter the Extension Phase in which they will continue to receive their CAB LA + RPV LA regimen. In addition, RAMOS NG will facilitate the initial supply and subsequent resupply of IP to study sites.

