9.1. Sample Size Considerations

. This study will randomize approximately 510 participants per arm. Assuming the true proportion with HIV-1 RNA ≥ 50 c/mL is 3% for the Q8W arm and 2% for the Q4W arm, a non-inferiority margin of 4%, and a 2.5% one-sided significance level, this sample size would provide at least 85% power to show non-inferiority at Week 48 (using unpooled Z test statistic). With this sample size, 90% power would be achieved assuming a 1% treatment difference and true proportions with HIV-1 RNA ≥ 50 c/mL of 2.63% for the Q8W arm and 1.63% for the Q4W arm.

With 510 subjects per arm and assuming an observed proportion HIV-RNA ≥ 50 c/mL is 2% for Q4W, the largest observed treatment difference to achieve non-inferiority with respect to a 4% margin is 1.92 percentage points. This equates approximately to observing an excess of 10 subjects on the Q8W arm (10 subjects on Q4W vs. 20 subjects on Q8W).

This sample size of 510 participants per arm will also provide at least 90% power (using unpooled Z test statistic) to show non-inferiority in the proportion of participants with plasma HIV-1 RNA < 50 c/mL (per FDA's snapshot algorithm) at Week 48 over a range of true response rates, on the basis of a -10% non-inferiority margin and 2.5% one-sided significance level (see [Figure 15](#)). For example, assuming true response rate for the Q8W arm and Q4W arm are both 92%, the power is $\geq 99\%$ to show non-inferiority for this key secondary endpoint.

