9.2.2. Treatment Comparisons

9.2.2.1. Primary Comparison of Interest

The primary analysis will be based on the ITT-E population. The primary comparison will be made at a one-sided 2.5% level of significance. Treatment with Q8W will be declared non-inferior to Q4W if the upper end of a two-sided 95% confidence interval for the difference between the two groups (Q8W – Q4W) in the proportion of participants with HIV-RNA ≥ 50 c/mL at Week 48 (defined by the US FDA snapshot algorithm) lies below 4%.

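### With rare failures, the planned primary interval (CMH difference with Sato variance) runs above the stated one-sided 2.5% level: about 3.2% at the planning Q4W rate of 2%

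*Protocol*

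**What the plan says.** Protocol section 9.2.2.1: "The primary comparison will be made at a one-sided 2.5% level of significance".

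Section 9.3.1 fixes the method. The estimate is the CMH-weighted difference in failure proportions over three strata of prior CAB + RPV exposure. The two-sided 95% limits are the estimate plus or minus 1.96 standard errors, "using the variance estimator given by [Sato, 1989], which is consistent in both sparse data and large strata". The rule is: "Non-inferiority will be declared if the upper bound of the two-sided 95% confidence interval for the difference" (Q8W minus Q4W) is less than 4%. Only the algebra of the Sato variance is left to the analysis plan.

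Section 9.1 gives the design: "This study will randomize approximately 510 participants per arm", with a true HIV-1 RNA failure proportion that "is 3% for the Q8W arm and 2% for the Q4W arm, a non-inferiority margin of 4" percentage points. It concludes that "this sample size would provide at least 85% power to show non-inferiority at Week 48 (using unpooled Z test statistic"). A second scenario, 90% power, uses "2.63% for the Q8W arm and 1.63% for the Q4W arm". Section 6.2 sets the allocation: "Participants will be randomized in a 1:1 ratio".

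**The concern.** The interval takes its standard error at the observed rates, not at rates on the non-inferiority boundary. With few failures the two move together: a sample with a chance-low Q8W count has both a small difference and a small standard error. When Q8W is truly 4 points worse, the upper limit therefore falls below 4% more often than 2.5% of the time.

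Consistency, which section 9.3.1 gives as the reason for the Sato variance, is a large-sample property. It does not secure the tail probability at the event counts planned here. At the boundary with Q4W at 2%, those counts are about 510 × 0.02 = 10 failures on Q4W and 510 × 0.06 = 31 on Q8W.

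This is the trial's confirmatory test. It also gates the key secondary comparisons (section 9.2.2.2) and is repeated at Week 96 (section 9.3.2.2).

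**Working it through.** **Inputs.** n = 510 per arm, margin 4 points, planning rates 3% v 2%, one-sided 2.5% (sections 9.1 and 9.2.2.1); 1:1 allocation (section 6.2); multiplier 1.96 and decision rule (section 9.3.1). Stratum sizes are not given in the protocol, so several splits were assumed.

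**1. Reproduce the stated power.** Unpooled formula: power = Φ((0.04 − 0.01)/SE − 1.96).

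- 3% v 2%: SE = √(0.03×0.97/510 + 0.02×0.98/510) = 0.00977; 0.03/0.00977 = 3.07; Φ(1.11) = 86.7%.
- 2.63% v 1.63%: 91.3%.

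Exact binomial enumeration of the same rule gives 85.8% and 90.0%. The protocol's 85% and 90% are therefore correct for the planned rule.

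**2. Sato variance with one stratum and equal arms.** Let x and y be the Q8W and Q4W failures, p8 = x/n, p4 = y/n and d = p8 − p4. The Sato variance is (dP + Q)/W². Here P = (y − x)/4, Q = [x(n − y) + y(n − x)]/(4n) and W = n/2. Substituting gives [p8 + p4 − 2·p8·p4 − d²]/n = p8(1 − p8)/n + p4(1 − p4)/n, which is the unpooled variance. A numerical check agreed to rounding error.

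**3. Exact one-sided error.** For each true Q4W rate p, with Q8W at p + 4 points, sum the binomial probabilities of all count pairs with d + 1.96·SE < 0.04. The last column does the same for the Miettinen-Nurminen score rule at 4%.

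| True Q4W rate | Planned rule | Score rule |
|---|---|---|
| 0.25% | 4.22% | 2.00% |
| 0.5% | 4.04% | 2.07% |
| 0.87% (LATTE-2 Week 48, 1/115) | 3.75% | 2.22% |
| 1% | 3.66% | 2.26% |
| 2% (planning value) | 3.19% | 2.37% |
| 3% | 2.94% | 2.36% |
| 5% | 2.71% | 2.39% |
| 10% | 2.58% | 2.50% |

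The mechanism shows at the pass threshold. With true rates of 6% and 2% the standard error is √(0.06×0.94/510 + 0.02×0.98/510) = 1.22 points. At the just-passing result of 19 v 10 failures the estimated standard error is only 1.04 points.

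**4. Stratification.** The three-stratum CMH/Sato rule was simulated (1,000,000 runs per setting) under assumed splits of 33/33/33, 55/10/35, 40/15/45 and 70/5/25 per cent. The error was 3.16% to 3.20% at Q4W 2%, 3.64% to 3.67% at 1% and 4.03% to 4.05% at 0.5%. Stratifying neither helps nor harms, so the unknown stratum sizes matter little.

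**5. Power at a true 2.5% level, 510 per arm.**

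| Rule | Error at Q4W 2% | Power 3% v 2% | Power 2.63% v 1.63% |
|---|---|---|---|
| Planned (1.96 × Sato SE) | 3.19% | 85.8% | 90.0% |
| Sato, multiplier 2.08 | 2.50% | 82.7% | not computed |
| Score | 2.37% | 81.2% | 85.5% |

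The 2.08 multiplier is calibrated only at Q4W 2%; at 1% its error is 2.72%.

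**6. Effect on decisions.** Largest Q8W failure count that still passes:

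| Q4W failures | 0 | 3 | 7 | 10 | 13 |
|---|---|---|---|---|---|
| Planned rule | 13 | 15 | 17 | 19 | 22 |
| Score rule | 11 | 13 | 16 | 19 | 21 |

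**The case against.** **The range depends on the Q4W rate.** A reader might infer that the error is 3.2% to 4.2% whatever happens. It is not: at Q4W rates of 3% to 5% it is 2.9% to 2.7%. The 4.2% end needs a Q4W rate of 0.25%, which is 510 × 0.0025 = about one expected failure and is not a planning value. This stands, and the range must be read with its condition. Low rates are still within the protocol's own view. Section 9.1.2 reports 1/115 (Week 48) and 0/115 (Week 96) for Q4W in LATTE-2, and says proportions could be lower still in this trial.

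**The power statement is not an error.** A reader might infer that the 85% is miscalculated. It is not. Section 9.1 names the unpooled test, section 9.1.4 says the calculation is asymptotic, and the planned rule delivers 85.8%. Nor is the whole fall to 81.2% removed excess, because the score rule is itself slightly conservative (2.37% at Q4W 2%). Recalibrating Sato gives 82.7%, so the part due to the excess is about 3 points.

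**The sentence on the Sato variance is true, and 2.5% is nominal.** This also stands: there is no contradiction in the text. But the level is stated without qualification for the one confirmatory test, and the chosen interval exceeds it at the planning rate.

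**The practical difference is small.** The threshold moves by at most two Q8W failures, and at the planned 10 Q4W failures it does not move at all. This limits the severity.

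**Futility is ignored.** The IDMC futility analysis (sections 4.2.6 and 9.2.3.2) could only lower the chance of a false declaration. Its rule is left to the charter, so the reduction cannot be computed and cannot be relied on to restore 2.5%.

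**Conclusion.** The point holds, conditional on rare failures. At the planning rate the true one-sided error is 3.2% against a stated 2.5%, a relative excess of 28% (3.19/2.5). It rises to 3.7% at a Q4W rate of 1% and 4.0% to 4.2% at 0.5% to 0.25%, and fades at 3% and above. Power at 3% v 2% for a test that holds 2.5% is about 81% (score) to 83% (Sato recalibrated at Q4W 2%).

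These figures assume 510 analysed per arm, independent binomial outcomes, a true difference of exactly 4 points and no futility stop. Severity is moderate: the error statement on the sole confirmatory test is wrong, but the decision boundary shifts by only 0 to 2 participants.

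**What to change.** Before any data by treatment arm are reviewed (section 9.2.3 places this before the Week 24 database freeze):

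- In section 9.3.1, replace the Sato-variance limits by stratified Miettinen-Nurminen (score) limits at the 4% margin, with the same CMH weights and strata. Apply this at Week 48 and to the Week 96 repeat in section 9.3.2.2.
- Keep the Sato interval as a pre-specified sensitivity analysis.
- In sections 1.3, 4.1 and 9.1, restate power as about 81% at 3% v 2%, and in section 9.1 as about 85.5% at 2.63% v 1.63%, with N unchanged.
- Section 9.3.2.1 borrows its interval from 9.3.1, so say explicitly which interval the key secondary comparison uses.

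The cost is wording, one standard procedure and about 4 to 5 points of stated power; no further participants are needed. Restoring an exact 85% at 3% v 2% with the score rule would take about 570 per arm, which is not proposed.

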9.3.2. Secondary Analyses

9.3.2.1. Key Secondary Efficacy Analysis

A key secondary analysis will evaluate the proportion of participants with HIV-1 RNA <50 c/mL (according to the FDA's Snapshot algorithm) at Week 48 for the ITT-E population. Participants with last available HIV-1 RNA measurement less than 50 copies/mL while the participant is on treatment within the analysis visit window of interest are classified as responders; participants without evaluable HIV-RNA data for the visit of interest or who change treatment not permitted per protocol before the analysis window are considered non-responders. Full details on the Snapshot algorithm for computation of the proportion with HIV-1 RNA < 50 copies/mL will be contained in the RAP. The adjusted difference between the randomized arms for the proportions (Q8W – Q4W) and its confidence interval will be calculated according to a stratified analysis with Cochran-Mantel Haenszel (CMH) weights, as described for primary endpoint (Section 9.3.1).

A non-inferiority margin of -10% will be used for this secondary comparison, where if the lower limit of the 95% confidence interval (CI) of the difference between the rates (Q8W – Q4W) is greater than -10%, non-inferiority will be demonstrated.

9.3.2.2. Other Secondary Endpoint Analyses

The primary analysis (Section 9.3.1) and key secondary efficacy analysis (Section 9.3.2.1) will be repeated at Week 96, with the only difference being a change in time point from Week 48 to Week 96 for determining the snapshot outcomes.

For the Week 24 planned analyses, the adjusted treatment difference in proportion of participants with plasma HIV-1 RNA ≥ 50 c/mL (FDA Snapshot algorithm, with 95% confidence interval) at Week 24 will be calculated using the methodology described in Section 9.3.1, but no formal test of non-inferiority will be performed at this early timepoint.

Proportion of participants with plasma HIV-1 RNA ≥ 50 c/mL and HIV-1 RNA < 50 c/mL (FDA Snapshot algorithm) at Week 24, Week 48 and Week 96 respectively, will be summarized using the Snapshot algorithm for the ITT-E population. Proportion of participants with confirmed virologic failures will also be summarized over time.

Absolute values and change from Baseline in CD4+ lymphocyte count will be summarized over time including Week 48 and Week 96.

The proportion of participants with HIV-1 RNA ≥ 50 c/mL based on the snapshot algorithm, will be summarized at Week 24, Week 48 and Week 96 by duration of prior CAB + RPV exposure (0 weeks, 1-24 weeks, >24 weeks).

The proportion of participants with HIV-1 RNA < 50 c/mL based on snapshot algorithm, will be summarized at Week 48 and Week 96 by duration of prior CAB + RPV exposure (0 weeks, 1-24 weeks, >24 weeks).

An observed case dataset, with no imputation for missing data, will be the primary dataset used for analysis of safety endpoints.

The proportion of participants reporting AEs will be tabulated for each treatment group. The following summaries of AEs will be provided:

- Incidence and severity of all AEs
- Incidence and severity of treatment related AEs
- Incidence and severity of AEs leading to withdrawal
- Incidence of SAEs

Changes from baseline in laboratory will be summarized by visit and treatment group including Week 48 and Week 96. In addition, the number and percentage of participants with graded laboratory toxicities (based on DAIDS categories) will be summarized by treatment group.

Further details for secondary efficacy, safety, and exploratory endpoint analyses will be included in the RAP.

9.3.3. Pharmacokinetic Analyses

The GSK Division of Clinical Pharmacology Modeling and Simulation (CPMS) will be responsible for the PK analysis of CAB. The Division of Clinical Pharmacology Development at Janssen Research and Development will be responsible for conduct or oversight of the PK analysis for RPV.

Actual sampling and dosing times as recorded in the eCRF will be used for analysis.

Plasma CAB and RPV concentration data will be listed and summarized by week, day, and planned sampling time in both tabular and graphical forms. A composite predose (C0) concentration may be estimated for purposes of PK/PD analysis. Post hoc estimates of PK parameters will be determined by population PK modeling separately (see Population PK Analysis below).

9.3.4. Population PK Analysis:

CAB LA and RPV LA population PK models will be constructed separately and individual Bayesian PK parameter estimates may be obtained, if the quality of the data permits. Data from this study may be merged with previous data to support the model building process. Sources of variability in pharmacokinetic parameters will be investigated during population modeling. Demographic parameters including, but not limited to age, gender, ethnic origin, body size (weight, height, body surface area, body mass index), and relevant laboratory parameters will be evaluated as potential predictors of inter- and intra-participant variability for pharmacokinetic parameters. Population pharmacokinetic modeling will be performed using the non-linear mixed effects software NONMEM (ICON; Hanover, MD). Further details of population pharmacokinetic analyses will be described in a separate RAP. Population PK analyses will be done under separate Population-PK Reporting and Analysis Plans, and post hoc PK parameters may be determined.

